Atrial fibrillation or atrial flutter	Grade 1 or 2	Maintain ibrutinib dose level	Maintain copanlisib dose level
	Grade 3 (Symptomatic and incompletely controlled with medications or device)	Omit ibrutinib dose until resolved to ≤ Grade 1, then resume at reduce 1 dose level Third recurrence: off study	Dose adjustments of copanlisib per investigator discretion
	Grade 4	Discontinue ibrutinib	Discontinue copanlisib
May dose modify/hold copanlisib, ibrutinib or both as clinically indicated			
OTHER CARDIAC DISORDERS	Grade 1 or 2	Omit dose until resolved to ≤ Grade 1, then reduce 1 dose level	
	Grade ≥ 3	Off study	
SKIN	May dose modify/hold copanlisib, ibrutinib, or both based on association with rash		
Rash	Grade 1 (<10% body surface area BSA; no associated erythema or pruritus)	Maintain ibrutinib dose level Consider to initiate appropriate skin toxicity therapy, e.g. with topical corticosteroids B.I.D. and oral antihistamines	Maintain copanlisib dose level
	Grade 2 (10 to 30% BSA and associated with erythema or pruritus; limited instrumental activities of daily living (ADL))	
Tolerable Grade 2:
 
 • Initiate/intensify appropriate skin toxicity therapy, e.g. with topical steroids B.I.D. and oral antihistamines. • Maintain ibrutinib level. 
Intolerable Grade 2 (if considered associated with ibrutinib):
 
 • Omit ibrutinib dose and initiate/intensify appropriate skin toxicity therapy, e.g. with topical steroids B.I.D., oral antihistamines and oral steroids. 
First occurrence:
 
 • If resolved to grade ≤ 1 in ≤ 2 weeks, maintain dose level. • If resolved grade ≤ 1 in more than 2 weeks, ↓ 1 dose level. 	
Tolerable Grade 2:
 
 • Initiate/intensify appropriate skin toxicity therapy, e.g. with topical steroids B.I.D. and oral antihistamines. • Maintain copanlisib level. 
Intolerable Grade 2 (if considered associated with copanlisib):
 
 • First occurrence: Delay infusion until resolved to ≤ Grade 1, maintain dose level • Second and Third occurrence: Delay infusion until resolved to ≤ Grade 1, decrease by one dose level • Fourth occurrence: Discontinue • Start skin directed therapy

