		
 Consider continuing skin toxicity therapy up to 2 weeks after re-introduction of ibrutinib. In case of flare after cessation of skin toxicity therapy, consider prompt re-implementation. 
Second occurrence: Omit ibrutinib dose and follow treatment guidance above.
 
 Once resolved to grade ≤ 1, reduce ibrutinib 1 dose level 
According to the investigators discretion, a paired skin biopsy could be obtained (from both an affected and an unaffected skin area for local histopathology assessment) if clinical appropriate.
	
	Grade 3 (Non-macular, papular rash covering $>30\%$ BSA with or without symptoms)	
 Initiate/intensify appropriate skin toxicity therapy, e.g. with topical steroids B.I.D., oral antihistamines and oral steroids. May continue ibrutinib with short term follow up of rash to monitor for improvement If rash does not improve after 5 days on intensified approach, then consider stopping ibrutinib. Once resolved to grade ≤ 1, consider reducing ibrutinib 1 dose level. Consider continuing skin toxicity therapy up to 2 weeks after re-introduction of ibrutinib. In case of flare after cessation of skin toxicity therapy, consider prompt re-implementation. 	
 Initiate/intensify appropriate skin toxicity therapy, e.g. with topical steroids B.I.D., oral antihistamines and oral steroids. May proceed with copanlisib infusion with short term follow up of rash to monitor for improvement If rash does not improve after 5 days on intensified approach, then delay infusion of copanlisib. Consider continuing skin toxicity therapy up to 2 weeks after re-introduction of ibrutinib. In case of flare after cessation of skin toxicity therapy, consider prompt re-implementation. First occurrence: Delay infusion until resolves to \leq Grade 1, decrease by one dose level Second occurrence: Delay infusion until resolves to \leq Grade 1, decrease by one dose level Third occurrence: Discontinue

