	Grade 3 (Macules or papules covering $>30\%$ BSA with or without symptoms)	
 Omit ibrutinib dose and initiate/intensify appropriate skin toxicity therapy, e.g. with topical steroids B.I.D., oral antihistamines and oral steroids. Once resolved to grade ≤ 1, reduce ibrutinib 1 dose level. Consider continuing skin toxicity therapy up to 2 weeks after re-introduction of ibrutinib. In case of flare after cessation of skin toxicity therapy, consider prompt re-implementation. 	First occurrence: Delay infusion until resolves to \leq Grade 1, decrease by one dose level Second occurrence: Delay infusion until resolves to \leq Grade 1, decrease by one dose level Third occurrence: Discontinue

		According to the investigators discretion, a paired skin biopsy could be obtained (from both an affected and an unaffected skin area for local histopathology assessment) if clinical appropriate.	
	Grade 4 (including other skin toxicity than maculo-papular rash)	Discontinue ibrutinib According to the investigators discretion, a paired skin biopsy could be obtained (from both an affected and an unaffected skin area for local histopathology assessment) if clinical appropriate.	Discontinue copanlisib
GENERAL	May dose modify/hold copanlisib, ibrutinib or both as clinically indicated		
Fatigue	Grade 1 or 2	Maintain dose level	
	Grade 3	Omit dose until resolves to ≤ Grade 1, then: If resolved ≤ 7 days, then maintain dose level If resolved > 7 days, then reduce 1 dose level	
	Grade 4	Discontinue therapy	
OTHER NON-HEMATOLOGIC EVENTS	May dose modify/hold copanlisib, ibrutinib or both as clinically indicated		
	Grade 1 or 2	Maintain dose level	
	Grade 3	Omit dose If resolved ≤ 7 days, then maintain dose level If resolved > 7 days, then reduce 1 dose level	
	Grade 4	Discontinue therapy	

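### Table 9-7: the two Grade 3 rash rows overlap for a purely papular rash and give different instructions, and the copanlisib cell of the first row does not say when its delay-and-reduce steps begin

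*Combined protocol and SAP*

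**What the plan says.** Within the Rash entry of Table 9-7, the first Grade 3 row is labelled "Non-macular, papular rash covering" more than 30% of body surface area. The second is labelled "Macules or papules covering" the same extent. Both apply with or without symptoms.

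For ibrutinib, the first row says "May continue ibrutinib with short term follow up of rash to monitor for improvement"; stopping is to be considered if five days of intensified skin treatment bring no improvement, and a one-level reduction is to be considered after resolution. The second row says "Omit ibrutinib dose and initiate/intensify appropriate skin toxicity therapy", with a one-level reduction once the rash is at Grade 1 or lower.

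For copanlisib, the first row says "May proceed with copanlisib infusion with short term follow up of rash to monitor for improvement", and then "If rash does not improve after 5 days on intensified approach, then delay infusion of copanlisib". Further down the same cell is a ladder that opens with "First occurrence: Delay infusion until resolves to" Grade 1 or lower and a drop of one dose level. The second occurrence is handled the same way, and the third ends copanlisib. The second row contains only that ladder.

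The line that opens the skin section reads "May dose modify/hold copanlisib, ibrutinib, or both based on association with rash". A note at the end of the table says that where a toxicity is associated with one drug, the investigator is required to hold and reduce that drug and may continue or modify the other. The text of Section 9.7 before the table says that, in the expansion phase, doses have to be held according to these guidelines.

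**The concern.** A dose-modification table should give one instruction per drug for each event. Here a rash made up only of papules satisfies two row labels with different actions, and one cell leaves the order of its own steps unstated. Two investigators could read the table carefully and treat the same patient differently: one continues both drugs under observation, the other holds both and then reduces them.

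The choice of row matters first for patient safety and for consistent dose intensity. It also matters for the dose-reduction rules of Section 9.7, which allow at most two reductions per drug and end therapy if the same toxicity returns at the same or worse severity after resumption at a lower dose. Whether a first Grade 3 rash uses up a reduction therefore affects what a recurrence leads to. Sections 11.5 and 11.7 list rash among the likely toxicities (above 20%) of each drug, so the skin part of the table will be used, although not necessarily these two rows.

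**Working it through.** There is no figure to reproduce; the check is a comparison of text. Take a first-occurrence, purely papular rash over more than 30% of body surface area.

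| | First Grade 3 row | Second Grade 3 row |
|---|---|---|
| Does the rash meet the label? | Yes: papular, no macules | Yes: papules are sufficient |
| Ibrutinib | May continue; consider stopping after five days without improvement; consider reducing | Omit, then reduce one level |
| Copanlisib | May proceed; delay after five days without improvement; ladder also listed | Ladder only: delay, then reduce one level |

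**Step 1, how wide the overlap is.** Extent and symptom qualifier are identical, so only the description of the rash separates the rows. The word non-macular keeps any rash with macules out of the first row. Macular and maculopapular rashes therefore go to the second row only. The overlap is confined to purely papular rash.

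**Step 2, ibrutinib.** The two cells differ directly: permission to continue against an instruction to omit and then reduce.

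**Step 3, copanlisib between rows.** The occurrence ladders are the same in both rows. The difference is the permission to proceed, which the second row does not contain.

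**Step 4, copanlisib within the first row.** The ladder can be read in two ways: it starts at once, or only after the five-day step has led to a delay. No words connect the two. In the second row the same ladder stands without any condition.

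**Step 5, whether other text settles it.**
- The opening skin line gives general discretion but does not choose a row.
- The skin-toxicity guidance in Section 9.8 does not choose one either.
- The closing note on holding and reducing the associated drug sits against both permissions in the first row.

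**Step 6, size.** A reader might take 20% of 33 phase II patients, 0.20 × 33 = 6.6 or about 7, as the number affected. That counts rash of any grade. Grades 1 and 2 have their own rows. Neither the Grade 3 share nor the purely papular share is given, so the number reaching the overlap cannot be derived.

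**Step 7, dose difference for one patient.** Table 9-6 starts reductions from the treating dose, and Table 9-2 leaves three possible levels. One level down would mean:
- dose level 2: copanlisib 60 to 45 mg, ibrutinib 560 to 420 mg;
- dose level 1: copanlisib 45 to 30 mg, ibrutinib 560 to 420 mg;
- dose level -1: copanlisib 45 to 30 mg, ibrutinib 420 to 280 mg.

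The contrast of 60 to 45 mg with 560 to 420 mg therefore assumes that dose level 2 becomes the phase II dose.

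**The case against.** The strongest reply is that sensible reading resolves most of this.

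- **The copanlisib cell as a sequence.** Treat the skin, proceed under observation, delay if five days bring no improvement, then use the ladder to decide how the delay ends and at what dose. This is a natural reading, and on it the cell does not contradict itself. A reader might infer that the cell orders the infusion both to proceed and to be delayed; the text does not establish that. What stands is that the link is unstated.
- **The row labels.** The first label may have been meant to cover rash that is not maculopapular, and the second maculopapular rash. The Grade 4 row, which mentions skin toxicity other than maculo-papular rash, hints at such a split. It would separate the rows, but the labels as written do not say it.
- **Permission is not conflict.** The first row is permissive. An investigator who holds and reduces as in the second row breaches none of its permissions, so calling the rows opposite is too strong. The reverse does not hold: an investigator who continues ibrutinib under the first row departs from the second.
- **Narrowness.** Section 9.8 names maculopapular rash among the most frequent skin events, and those rashes are unaffected by the overlap. This stands and limits the size.

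The sequential reading leaves the row overlap, and the relabelling leaves the gap inside the cell. Adopting both would remove those two problems, but neither is written down, and the closing note would still need to be squared with the permissions.

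**Conclusion.** The point holds for a purely papular Grade 3 rash. The ibrutinib instructions of the two rows conflict, the copanlisib instructions differ in the permission to proceed, the start of the first row's ladder is unspecified, and the closing note does not fit the permissive wording. This rests on reading the row labels literally. The number of patients affected is unknown and may be small.

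Several stronger conclusions are tempting but not supported:

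- **That any Grade 3 rash can be either treated through or held.** The word non-macular rules that out for the overlap.
- **That both drugs necessarily drop a level on the stricter path.** The closing note requires action on the associated drug and leaves the other to discretion.
- **That event-free survival is directly altered.** Neither Grade 3 ibrutinib cell calls for permanent discontinuation, and the copanlisib ladders are the same. A difference could arise only indirectly, through the recurrence rule of Section 9.7 and the counting of discontinuation for adverse events in Section 14.2; that endpoint is secondary.
- **That the phase I results are at stake.** Section 9.2 counts an adverse event causing a delay of more than 7 consecutive days in cycle 1 as dose-limiting, but the table is introduced for the expansion phase with reductions after cycle 1, so any such effect is secondary.

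No effect on the primary complete-response endpoint or the two-stage decision is shown. This is a wording inconsistency in a safety rule that should be corrected, not a fault in the statistical design.

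**What to change.** The sponsor should make three linked edits to Table 9-7:

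1. Redefine the two Grade 3 rash rows so that no rash meets both labels.
2. In the first row's copanlisib cell, state whether the occurrence ladder applies at once or only after the five-day step.
3. Align both rows with the closing note on holding and reducing the associated drug.

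The test of the result is that each Grade 3 rash leads to one instruction per drug. Which instruction that should be is a clinical decision for the sponsor and investigator, and this review proposes none. The cost is an amendment to protocol wording, with no change to sample size, endpoints or analysis.

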4.3 Intervention

Treatment will be with intravenous copanlisib on days 1, 8, 15 of 28 day cycles and oral ibrutinib daily in 28 day cycles. A cycle is defined as 28 days of therapy. If patients are in a CR by RECIL criteria, copanlisib will be held after 2 cycles of combination past a CR or minimum of 6 cycles of therapy. Copanlisib will be restarted upon radiographic and pathologic progression of disease (see Section 9.9). Patients remain on continuous ibrutinib if copanlisib is held. It may then be restarted as clinically indicated. Therapy will continue until disease progression, intolerable toxicities or death with a maximum duration of treatment of 36 cycles not exceeding 36 months on therapy.

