10.2. Treatment period

Patients will receive study treatments copanlisib and ibrutinib until disease progression, unacceptable toxicity or until other discontinuation criteria are met, whichever come first. Maximum duration of treatment is 36 cycles not exceeding 36 months.

Patients will follow the visit schedule as per Table 10-1. Permitted visit windows for assessments within the treatment period and at efficacy follow-up visits are included in the table. If copanlisib is held based on achievement of a complete response, patient visits will be every 2 cycles during C1-C6, every 3 cycles during C7-C12, every 4 cycles during C13-36.

Information on drug exposure will be collected on the Dosage Administration Record eCRF. Concomitant medications/significant non-drug therapies prior to start (\leq 28 days) and after start of study treatment will be recorded on the appropriate eCRFs.

Compliance will be assessed by the investigator and/or study personnel at each visit using box counts and information provided by the caregiver.

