11.7. Copanlisib anticipated toxicities

The side effects listed below have been reported by patients who have received copanlisib in clinical trials

Likely (>20%): Anemia, hyperglycemia, hypertension, fatigue, nausea, diarrhea, neutropenia (including febrile neutropenia), infections, rash (including macular, maculopapular, pruritic, pustular, erythematous, generalized, exfoliative rash, pruritus/Pruritus generalized, dermatitis acneiform, dermatitis allergic and dermatitis exfoliative)

Less Likely (4-20%): Dysgeusia, leukopenia, lymphopenia, elevated amylase and lipase increased, hypomagnesemia, hyponatremia, paraesthesia, pneumonitis, interstitial lung disease, thrombocytopenia, vomiting, chills, mucosal inflammation (including stomatitis and mouth ulceration), dry mouth, muscle spasms

Rarely (<3%): alopecia, hyperinsulinemia, infusion related reaction, hypersensitivity, gastritis, colitis, aphthous ulcer, eosinophilia, Pancreatitis, Stevens-Johnson syndrome

Most side effects listed above have been mild to moderate in severity; however severe side effects have occurred. Some side effects have been severe enough to lead to study drug discontinuation, dose modification or reduction, hospitalization, disability and sometimes death.

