13.0 CRITERIA FOR REMOVAL FROM STUDY

Patients may voluntarily withdraw from the study or be removed from the study at the discretion of the investigator at any time. Patients may be withdrawn from the study if any of the following occur:

- Disease progression. However, if progression develops after CR while patient is on ibrutinib alone, patients could restart treatment upon radiographic and pathologic expression of disease.
- Ineligibility (at the pretreatment evaluation) of the patient as defined in the inclusion/ exclusion criteria
- Treatment will be discontinued at the request of the patient, refusal of therapy, non-compliance, or upon the development of an intercurrent significant medical illness.
- Significant protocol violation
- Unacceptable toxicity
 - Grade 4 arterial hypertension
 - Grade 4 dermatologic toxicity
 - Non-infectious pneumonitis
 - Drug induced clinically relevant pancreatitis
 - Grade ≥ 3 hypersensitivity reaction
- Decision by the investigator that termination is in the patient's best medical interest.
- Loss to follow-up

- Development of active HBV or HCV infection, hepatitis, or HIV infection
- Pregnancy or a positive pregnancy test
- Death of the patient

In addition to the general study treatment withdrawal criteria, the following study specific criteria will also require premature study treatment discontinuation:

- Use of prohibited medication
- Start of any other anti-neoplastic therapy

If a study treatment withdrawal occurs, or if the patient fails to return for visits, the investigator must determine the primary reason for a patient's premature withdrawal from study treatment and record this information on the End of Treatment CRF page.

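### A Grade 3 hypersensitivity reaction has no single instruction: Sections 13 and 10.2, the Table 9-7 catch-all row and a note to that table do not agree

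*Combined protocol and SAP*

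**What the plan says.** Section 13 opens its list of reasons for removal with "Patients may be withdrawn from the study if any of the following occur". Under unacceptable toxicity the list includes "Grade ≥ 3 hypersensitivity reaction". Further down, the same section introduces two more criteria with "the following study specific criteria will also require premature study treatment discontinuation".

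Section 10.2 states: "Patients will receive study treatments copanlisib and ibrutinib until disease progression, unacceptable toxicity or until other discontinuation criteria are met, whichever come first". Section 4.3 is similar: "Therapy will continue until disease progression, intolerable toxicities or death".

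Table 9-7 in Section 9.7 gives dose modifications by toxicity and grade. For Grade 3 in the row for other non-hematologic events it says "Omit dose If resolved ≤ 7 days, then maintain dose level", and it lowers the dose by one level if resolution takes more than 7 days. Grade 4 in that row stops therapy. A note at the end of the table adds that, where a toxicity is associated with one drug, the investigator is obliged to hold that drug and reduce it.

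The event is an anticipated one. Section 11.7 lists "infusion related reaction, hypersensitivity" among the rare copanlisib toxicities (<3%).

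**The concern.** An investigator facing a Grade 3 hypersensitivity reaction can find three answers in the same protocol. Sections 13 and 10.2, read together, point to the end of treatment. The Table 9-7 row that catches the event points to resumption, at the same dose level if it resolved within 7 days. The note to the table points to a reduced dose of the responsible drug.

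Safety comes first: following the table as written can re-expose a patient whom Sections 13 and 10.2 would take off treatment. There is also an endpoint consequence. Section 14.2 counts treatment discontinuation for an adverse event as an event in event-free survival, so the same reaction is an event under one instruction and not under the others.

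**Working it through.** The point is a comparison of rules, and the plan gives no figure to reproduce. The only arithmetic concerns how often the event could arise.

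1. **Is there a dedicated row?** Table 9-7 covers anemia, neutropenia, thrombocytopenia, bleeding, creatinine, pneumonitis, bilirubin, AST/ALT, pancreatitis, hyperglycemia, hypertension, left ventricular dysfunction, QTc, atrial fibrillation or flutter, other cardiac disorders, rash, fatigue and other non-hematologic events. None is for hypersensitivity or infusion reactions, and Section 9.8 has no management guideline for them. Section 13 names five unacceptable toxicities. Four of these types (hypertension, skin, pneumonitis, pancreatitis) have a row; hypersensitivity is the one that does not.

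2. **Where does the event land?** A purely cutaneous reaction can be handled under the rash rows. A non-cutaneous reaction has only the row for other non-hematologic events.

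3. **The instructions side by side, for a non-cutaneous reaction:**

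| Source | Grade 3 | Grade 4 |
|---|---|---|
| Sections 13 and 10.2 together | Unacceptable toxicity; treatment runs until then (Section 13 itself says may) | Same |
| Table 9-7, other non-hematologic events | Omit; same level if resolved in 7 days or less, one level lower if later | Stop |
| Closing note to Table 9-7 | Hold and reduce the drug associated with the toxicity | Not needed, since the row stops therapy |

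 Grade 4 agrees. Grade 3 does not.

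4. **Scope.** Section 9.7 says that these reduction steps are for expansion-phase patients and can be followed after cycle 1. In phase I, Grade 3 or higher non-hematologic events in cycle 1 are dose-limiting toxicities under Section 9.2, with listed exceptions. Table 9-3 plans 33 phase II patients, of whom 6 come from phase I, so 33 − 6 = 27 are newly enrolled in the expansion.

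5. **How many patients?** Section 11.7 gives <3% for each of the two copanlisib terms, without a breakdown by grade.
 - At the ceiling for one term, the expected number of any grade is below 0.03 × 27 = 0.81 (or 0.03 × 33 = 0.99).
 - If both terms sat at the ceiling and never overlapped, these would double to 1.62 and 1.98.
 - Only the Grade 3 part is in conflict, and the documents give no copanlisib Grade 3 rate.
 - For ibrutinib alone, Section 3.0 reports one Grade 3 allergic hypersensitivity among 56 phase I patients (1/56 = 1.8%), in a patient with a history of drug hypersensitivity. Applied to 27 patients this is 27/56 = 0.48.

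**The case against.** The best reply is that nothing in the text compels a patient to be stopped. Section 13 says may. Section 10.2 neither defines unacceptable toxicity nor points to Section 13. Section 9.7 uses the same term without ending treatment at once: discontinuation follows when the toxicity has not resolved after a 28-day delay, with an exception for patients who are clearly benefiting. The catch-all row is itself headed as optional, and the notes let the investigator remove a patient for any toxicity. On this view an investigator can apply the specific entry in Section 13 ahead of a generic row, and only a cross-reference is missing.

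Much of this stands. A reader might infer that Sections 13 and 10.2 make stopping mandatory and that the protocol flatly contradicts itself. The wording just described makes mandatory stopping an inference, although Section 10.2 has no may and the word also in Section 13's later sentence supports that inference. What the reply does not do is supply one instruction. Permission to stop is not a direction to stop, and the Grade 3 cell still points to resumption.

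A reader might also infer that the plan orders re-infusion at the same dose and requires a reduction only after a second reaction. The documents do not support that. The closing note requires reduction of the associated drug at the first event, and the row itself reduces when resolution takes more than 7 days. Nor do the documents say how quickly such reactions resolve.

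**Conclusion.** The concern holds as an inconsistency between passages: for a non-cutaneous Grade 3 hypersensitivity reaction after cycle 1 in the expansion phase, the protocol offers three instructions that do not agree. It is not shown that any one of them is the binding rule.

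The size is small, probably one patient at most. That rests on the <3% category in Section 11.7 and on the assumption that Grade 3 events are a minority of those of any grade. A reader might want to turn the <3% into a probability that the trial meets the problem. That would describe reactions of any grade, it would need a lower rate that the documents do not give, and counting all 45 treated patients would include phase I patients outside the scope of these steps.

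The endpoint effect is limited to event-free survival. A reader might extend it to the primary endpoint, because continued treatment leaves a later complete response possible. However, nothing in Section 14.2 stops a complete response reached before withdrawal from counting as best response by 6 months. Safety is the main reason to act.

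**What to change.** Reconcile four places so that Grade 3 hypersensitivity has one instruction: Section 13 (including the permissive lead-in to its list), Section 10.2, the Grade 3 cell for other non-hematologic events in Table 9-7, and the closing note on the drug associated with a toxicity. This can be done with a separate row in Table 9-7 or with a cross-reference between the table and Section 13. The text should also say whether infusion-related reactions and purely cutaneous reactions are included. Which rule applies is a clinical decision for the sponsor, and this point does not favour one.

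The cost is a wording amendment of one row or cross-reference plus matching edits. Sample size, decision thresholds and analysis methods do not change.
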